5.1.1.1.4 Missing Data

General missing data handling conventions are specified for methodologies in Section 5.1.1.1.3 and summarized as follows:

Table 5–4 Missing Data Handling by Endpoint Type

Parameter type	Timing	Missing Data Handling
Responder	Double-blind Treatment Period	 All participants included unless otherwise specified Participants with no postbaseline values = nonresponders
Immunogenicity responder	Treatment Period	Participants with no postbaseline assessable values excluded
Time-to-event	Double-blind Treatment Period	 Participants not reporting specified event (intolerable diarrhea) during the Open-label Treatment Period excluded Participants with no postbaseline values = censored
CFB ANCOVA	Treatment Period	 If missing covariates (including baseline if applicable) Participant excluded If missing derived value at the specified postbaseline analysis visit: Participant excluded

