Primary Outcome Measure	ADA determinations from blood samples
Secondary Outcome Measures	AE reporting of recurrence (including date) of intolerable diarrhea after randomization to double-blind treatment following resolution of initial intolerable diarrhea. Assessments of efficacy [REDACTED] during open-label treatment, and during double-blind treatment.
[REDACTED]	[REDACTED]

Statistical Methods
	
Immunogenicity Assessments For each indication separately and combined, the number and percentage of patients meeting treatment-related ADA-positive status will be summarized, along with the 1-sided 95% Clopper-Pearson confidence interval, for Safety Population patients with at least 1 assessable postbaseline sample, ie, patients who are not postbaseline ADA undetermined (sample lost, damaged, or out of specifications). A sensitivity analysis will be performed where baseline ADA undetermined patients are excluded.
 
Efficacy [REDACTED] The efficacy [REDACTED] will be analyzed descriptively based on the Intent-to-Treat Population. As this is an open-label study, no inferential statistics will be performed.
 
[REDACTED]
 
[REDACTED]

-----------------------------------	--

[figure not shown]

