This will be a multicenter, open-label, long-term clinical study to assess the immunogenicity and long-term safety of linaclotide administered orally to adult patients with IBS-C or CIC, and to evaluate lower doses of linaclotide in patients who consider study withdrawal due to intolerable AEs that may be related to the use of linaclotide. Approximately 800 IBS-C or CIC patients (a minimum of 300 each) will be enrolled.

The study will consist of up to a 3-week Screening Period, followed by a 52-week Treatment Period (Figure 9.1–1). Patients who meet the entry criteria will receive once daily, open-label doses of 290 ug linaclotide for patients with IBS-C; those with CIC will receive once daily, open-label doses of 145 ug linaclotide.

In order to limit patient withdrawals from the study due to AEs and to gain information about the effect of lowering the dose in patients who experience intolerable AEs (defined as AEs that subjectively would cause a patient to consider study withdrawal), in particular diarrhea and other GI AEs that may be related to the use of linaclotide, the following intervention (Figure 9.1–2) will be offered as an optional treatment course to such patients, unless deemed clinically inappropriate by the Investigator:

1. A temporary suspension of dosing of up to 7 days. If the dose suspension needs to last longer than 7 days because the intolerable AE has not resolved, then the Investigator should contact the Study Physician to discuss the duration of the dose suspension or withdrawal of the patient from the study. All AEs resulting in the temporary suspension will be recorded on the eCRF.
2. After the intolerable AE has resolved, the patient will be randomized into a Double-blind Treatment Period via an interactive Web response system (IWRS) and will receive dose regimens specific to each indication as follows. If the randomized dose regimen is tolerated, the patient will remain on this dose for the duration of the study (total duration of linaclotide exposure [whether open-label or double-blind] is not to exceed 52 weeks).

IBS-C patients will be randomized in a 1:1:1 ratio to 1 of the following regimens:

- Linaclotide 290 ug every day
- Linaclotide 145 ug every day
- Linaclotide 72 ug every day

[figure not shown]
CIC patients will be randomized in a 1:1 ratio to 1 of the following regimens:

- Linaclotide 145 ug every day
 - Linaclotide 72 ug every day

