9.7 STATISTICAL METHODS AND DETERMINATION OF SAMPLE SIZE

9.7.1 Patient Populations

The following populations will be considered in the statistical analysis of the study.

9.7.1.1 *Screened Population*

The Screened Population will consist of all patients who sign an ICF for the study and receive a patient identification number.

9.7.1.2 *Safety Population*

The Safety Population will consist of all patients in the Screened Population who receive at least 1 dose of investigational product during the Treatment Period.

9.7.1.3 ***Intent-to-Treat Population***

The Intent-to-Treat (ITT) Population will consist of all patients in the Safety Population who have at least 1 postbaseline assessment for any efficacy or health outcomes parameter.

9.7.1.4 ***Randomized Population***

The Randomized Population will consist of all patients in the Safety Population who are randomized to double-blind investigational product following resolution of an intolerable AE.

9.7.1.5 ***Double-blind Safety Population***

The Double-blind Safety Population will consist of all patients in the Randomized Population who receive at least 1 dose of investigational product during the Double-blind Treatment Period.

9.7.1.6 ***Double-blind ITT Population***

The Double-blind ITT Population will consist of all patients in the Double-blind Safety Population who have at least 1 post-randomization assessment for any parameter during the Double-blind Treatment Period.

9.7.2 **Patient Disposition**

The number of patients in each of the study populations described in Section 9.7.1 will be summarized overall, by indication (IBS-C or CIC), and study center.

The number of screen failures (ie, patients who enter the Screening Period but not the Treatment Period) along with the associated reasons for failure will be tabulated overall.

The number and percentage of patients in the categories described in Table 9.7.2-1 will be summarized overall and by treatment group, if specified, for each indication in the Safety Population.

Table 9.7.2-1. Summarization of Patient Disposition

Category	By Treatment Group
Patients who complete the Open-label Treatment Period	No
Patients who prematurely discontinue during the Open-label Treatment Period	No
Reasons for premature discontinuation of open-label treatment as recorded on the eCRF	No
Patients who prematurely discontinue open-label treatment due to AE who do not randomize to double-blind treatment	No

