5.1.1.1.3 Statistical Methodology

The methodologies defined below apply as specified to individual endpoints defined in this SAP. When indicated, 95% 2-sided confidence intervals (CIs) and 2-sided p-values will be presented unless otherwise specified.

Table 5–3 Statistical Methodology

Methodology	Description	
Categorical counts	Number of participants in individual categories	
	\circ Participants with ≥ 1 qualifying event counted once per individual category	
Categorical	 Number and percentage of participants in individual categories 	
descriptives	\circ Participants with ≥ 1 qualifying event counted once per individual category	
	• (Optional if specified) N1 if percentage denominator ≠ number of participants in the	
	population (standard percentage denominator)	
	 N1 = participants with non-missing baseline value 	
	_	

Methodology	Description
	 Unevaluable assessments considered missing
	 If specified, participants with baseline PCS values will be excluded
	_
Continuous	• N1, mean, SD, median, minimum, maximum
descriptives	• N1 = participants with non-missing value
CFB descriptives	• Continuous descriptives for baseline, postbaseline, and change from baseline (CFB)
	values
	 N1 = participants with non-missing values at both baseline and the specified
	postbaseline analysis visit
CFB ANCOVA	 Continuous descriptives and SE for baseline, postbaseline, and CFB values
	 Estimates derived from ANCOVA model for CFB value controlling for fixed factors
	(treatment group) and fixed covariates (baseline value)
	Least squares (LS) means and standard errors
	LS mean differences, standard errors, and CIs vs highest LIN dose ¹ Description of the LIN dose of
	 P-values from contrast t-test comparing lower LIN doses² vs highest LIN dose¹
	• N1 = participants with non-missing values at both baseline and the specified
Responder	postbaseline analysis visit
Responder	 Categorical descriptives for responders and nonresponders Nonresponders include:
	Participants who do not meet responder criteria
	 Participants with no postbaseline values
	Risk differences and Wald CIs vs highest LIN dose ¹
	• Unadjusted risk ratios (RRs), odds ratios (ORs), and CIs vs highest LIN dose ¹
	• P-values from Fisher's exact test comparing lower LIN doses ² vs highest LIN dose ¹
Immunogenicity	Categorical descriptives for responders and nonresponders
responder	Nonresponders include:
1	Participants who do not meet responder criteria
	 Participants with no postbaseline values

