	Responder rate 1-sided 95% Clopper-Pearson CIs
	• N1 = all participants unless otherwise specified
Time-to-event	Categorical descriptives for participants with events and censoring
	 Censoring includes:
	 Participants who do not meet event criteria
	 Participants with no postbaseline values
	• Quartiles and CIs derived from Kaplan-Meier (KM) nonparametric model using log-
	log transformation of survivor function
	 Estimates derived from Cox proportional hazards model controlling for factor
	(treatment group)
	o Hazard ratios (HRs) and CIs vs highest LIN dose ¹
	• Estimates derived from log-rank model controlling for factor (treatment group)
	o P-values comparing lower LIN doses ² vs highest LIN dose ¹
173.4.C	N1 = all participants unless otherwise specified
KM figure	• Step-function figure of cumulative distribution function (1 – survivor function)
	estimates with censoring indicators, derived from KM nonparametric model

CFB = change from baseline; ANCOVA = analysis of covariance; TTE = time-to-event.

Methodology Description

Raw and derived data listings will be provided, and will be fully defined in the table, figure, and data listing specification document.

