5.1.1.3.3 Double-blind Treatment Period Analyses

A set of exploratory analyses will be conducted for Double-blind Safety Population participants, unless otherwise specified, for the subset of participants who experience an intolerable AE during the initial Open-label Treatment Period. Data from the Dose-reduced Open-label Treatment Period following discontinuation of double-blind treatment will be excluded from these analyses.

Pre-randomization (Double-blind Treatment Period baseline) values for efficacy endpoints are defined as the latest available assessment during the Treatment Period on or before the Double-blind start date.

[figure not shown]

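### By default, binary recurrence of intolerable diarrhea keeps patients who never had the index event, while time to recurrence excludes them

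*SAP*

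**What the plan says.** **Who is randomized.** Protocol 9.1 offers suspension and randomization for intolerable adverse events, "in particular diarrhea and other GI AEs that may be related to the use of linaclotide". Diarrhea is stressed but not required. The Randomized Population (Protocol 9.7.1.4) is "all patients in the Safety Population who are randomized to double-blind investigational product following resolution of an intolerable AE". SAP 5.1.1.3.3 runs the double-blind analyses in the Double-blind Safety Population, "for the subset of participants who experience an intolerable AE during the initial Open-label Treatment Period", again without a diarrhea condition.

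**What recurrence means.** The protocol synopsis lists, as a secondary outcome, "recurrence (including date) of intolerable diarrhea after randomization to double-blind treatment following resolution of initial intolerable diarrhea". SAP Table 4-1 has four endpoints for the dose-reduction objective: recurrence of diarrhea, recurrence of intolerable diarrhea, and the time to first occurrence of each.

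**Who is analyzed.** SAP Table 5-4 gives two rules for the same Double-blind Treatment Period:

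- Responder: "All participants included unless otherwise specified".
- Time-to-event: "Participants not reporting specified event (intolerable diarrhea) during the Open-label Treatment Period excluded".

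In SAP Table 5-3 the Responder nonresponders include "Participants who do not meet responder criteria". For time-to-event, Table 5-3 says "N1 = all participants unless otherwise specified", and Table 5-4 then specifies otherwise.

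**Protocol analysis.** Protocol 9.7.5 plans a Fisher exact test for recurrence, and Kaplan-Meier, log-rank and Cox analyses for time to recurrence. It restricts neither to patients with a prior episode.

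**The concern.** A patient randomized after, say, intolerable bloating, with no intolerable diarrhea before, cannot have a recurrence in the synopsis sense. The time-to-event rule removes such a patient. The visible default for binary endpoints keeps the patient, who then counts as a nonresponder. Two versions of one endpoint would then rest on different patients, and the visible text gives no reason for it.

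At stake is the only randomized comparison in the study: whether intolerable diarrhea returns less often on a lower dose. Patients not at risk in the denominator lower the rate in every arm and dilute the absolute difference.

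**Working it through.** **The plan's own figure.** The only sample-size figure is the one-sided 95% upper limit for 0 of 800 in SAP 5.1.2. It reproduces: 1 − 0.05^(1/800) = 0.3738%, stated as 0.374%. It concerns ADAs and does not bear on this point. No size or power is stated for the recurrence endpoints.

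**Which row applies.** The endpoint table of SAP 5.1.1.3.3 is not visible, so the link from binary recurrence to the Responder row is an inference. Protocol 9.7.5 names Fisher's exact test for recurrence, and Responder is the only method in the visible Table 5-3 that uses that test. Its timing in Table 5-4 is the Double-blind Treatment Period.

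**Dilution.** Let q be the share of an arm without open-label intolerable diarrhea, equal across arms and all counted as no recurrence. Let p_H and p_L be the recurrence rates among patients at risk, on the highest and the lower dose. With everyone kept:

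- observed rates: (1 − q)·p_H and (1 − q)·p_L
- risk difference: (1 − q)·(p_L − p_H)
- risk ratio: p_L / p_H, unchanged
- odds ratio: computed from the diluted rates, so closer to 1

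All inputs below are assumptions: p_H = 50%, p_L = 25%, 40 randomized per arm. Power is for the two-sided 5% Fisher test by full enumeration. It compares all 40 per arm with only the 40·(1 − q) at risk.

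| q | Observed rates | Risk difference | Risk ratio | Odds ratio | Power, all kept | Power, at risk only |
|---|---|---|---|---|---|---|
| 0 | 50% vs 25% | −25.0 | 0.50 | 0.33 | 56% | 56% |
| 10% | 45% vs 22.5% | −22.5 | 0.50 | 0.35 | 48% | 50% |
| 25% | 37.5% vs 18.8% | −18.8 | 0.50 | 0.38 | 38% | 41% |
| 40% | 30% vs 15% | −15.0 | 0.50 | 0.41 | 28% | 34% |
| 50% | 25% vs 12.5% | −12.5 | 0.50 | 0.43 | 22% | 27% |

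With 60% versus 30% assumed instead, power with all kept versus at risk only is 63% vs 64%, 48% vs 56%, 36% vs 47% and 28% vs 35% for q = 10%, 25%, 40% and 50%. Across both scenarios the loss is about 1 to 12 points.

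**One data example (assumed counts).** Events stay at 20 and 10, and patients not at risk are added to 40 at-risk patients per arm:

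- none added: 20/40 vs 10/40, Fisher p = 0.037
- 4 per arm (4/44, about 10%): 20/44 vs 10/44, p = 0.042
- 17 per arm (17/57, about 30%): 20/57 vs 10/57, p = 0.055

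**Unequal shares by chance.** If true recurrence is 40% in both arms, but q is 20% on the highest dose and 40% on the lower dose, the observed rates are 0.8 × 40% = 32% and 0.6 × 40% = 24%. This is a spurious difference of −8 points and a risk ratio of 0.75. Restricting both arms to patients at risk removes it.

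**The case against.** The strongest objection is that the deciding text cannot be seen. The Responder rule is a default that allows exceptions, and the place for an exception is the endpoint table of SAP 5.1.1.3.3. This SAP does put restrictions in endpoint tables: Table 5-28 limits the ADA endpoint to participants with an assessable postbaseline sample, although Table 5-3 would count those without postbaseline values as nonresponders. Text missing from the public copy is not missing from the plan. This stands, so the point has to be conditional. Against it, Table 5-4 itself writes out the exclusions for the ADA and time-to-event rows and writes none for Responder.

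Second, a reader might infer that all these patients are scored as free of recurrence on both binary endpoints. The documents do not support that. The synopsis requirement of a first episode concerns intolerable diarrhea only. Table 4-1 lists recurrence of diarrhea separately. A patient randomized for another event may have had tolerable diarrhea before, or may have a first diarrhea after randomization, and the visible text does not say how either is counted.

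Third, the effect is limited. The planned risk ratio is not diluted in expectation. At q = 10% the power loss is only 1 to 2 points, and the data example stays below 0.05. Protocol 9.4.4 names diarrhea as the most frequent adverse event and the most common reason for discontinuation, which points to a smaller rather than a larger q. Keeping every treated randomized patient is a defensible comparison, and the time-to-event analysis already gives the restricted answer. All of this stands, but it does not explain why two versions of one endpoint should differ in their denominators.

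**Conclusion.** The mismatch in the default rules is real. Unless SAP 5.1.1.3.3 overrides the default, binary recurrence of intolerable diarrhea includes patients who were never at risk of it as defined in the synopsis, while the time-to-event version does not.

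The consequence is a lower rate in each arm, a risk difference reduced by the fraction q, an odds ratio nearer 1 and some lost Fisher power. It would go too far to say that the dose effect is weakened on every scale, because the risk ratio is unchanged in expectation. It would also go too far to say that the plan certainly scores these patients as no recurrence.

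The figures are illustrations. They rest on assumed recurrence rates, arm sizes and q, on q being equal across arms except in the imbalance example, and on no counted event in the added patients. The documents give none of these quantities. SAP 5.1.1.3.3 calls the double-blind analyses exploratory, so the impact is modest and confined to the secondary dose-reduction objective. The primary ADA analysis is unaffected.

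**What to change.** 1. In the Responder row of SAP Table 5-4, apply the time-to-event exclusion to recurrence of intolerable diarrhea. The denominator becomes Double-blind Safety participants with intolerable diarrhea in the Open-label Treatment Period. Membership is fixed before randomization, so the comparison stays randomized. If SAP 5.1.1.3.3 already says this, a cross-reference in Table 5-4 is enough.
2. For the separate endpoint of recurrence of diarrhea, state one at-risk set and use it for both the binary and the time-to-event version. The exclusion in Table 5-4 names only intolerable diarrhea, so say whether it applies here too.
3. Report first-onset diarrhea in the other patients separately, as new onset.
4. Keep the all-participants result as a sensitivity analysis.

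The cost is a few lines of SAP wording and a smaller denominator for the binary endpoint. No new data are needed.

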5.1.1.1.5 Treatment Periods

The non-overlapping Open-label, Double-blind, and Dose-reduced Open-label treatment periods are defined by their respective treatment start and end dates. These 3 treatment periods are subsets of the overall Treatment Period. The start and end dates for each period are defined as follows:

Table 5–5 Treatment Period Definitions

Parameter	Start	End
Treatment Period	Treatment start date = first dose date of any	Treatment end date = last dose date of any
	LIN treatment	LIN treatment
Open-label	Open-label start date = first dose date of open-	Open-label end date = last dose date of open-
Treatment Period	label LIN treatment	label LIN treatment
	 Identical to treatment start date 	 Identical to treatment end date for
		participants who do not enter the
		Double-blind Treatment Period
Double-blind	Double-blind start date = first dose date of	Double-blind end date = last dose date of
Treatment Period	double-blind LIN treatment	double-blind LIN treatment
		 Identical to treatment end date for
		participants who do not enter the
		Dose-reduced Open-label Treatment
		Period

¹ Highest LIN dose by indication: IBS-C: LIN 290 μg; CIC: LIN 145 μg.

² Lower LIN doses by indication: IBS-C: LIN 72 μg, LIN 145 μg; CIC: LIN 72 μg.

Dose-reduced	Dose-reduced open-label start date = first dose	Dose-reduced open-label end date = last dose
Open-label	date of dose-reduced open-label LIN	date of open-label LIN treatment
Treatment Period	treatment	 Identical to treatment end date

5.1.1.2 Demographics

5.1.1.2.1 Analysis Populations

The distribution of participants within the analysis populations will be summarized as follows:

Table 5-6 Analysis Population Summaries

Parameter	Description	Timing	Methodology
Screened, Safety, and Intent-to-Treat (ITT) populations	Distribution overall and within sites in total and by indication	_	Categorical counts
Randomized, Double- blind Safety, and Double-blind ITT populations	Distribution overall and within sites in total and by treatment group within each indication	_	Categorical counts

5.1.1.2.2 Participant Disposition

Participant disposition encompasses the distribution of participants who enter, complete, and discontinue each specified period (epoch) as defined by study design, along with eCRF-reported discontinuation reasons from each respective period. Participant disposition will be summarized as follows:

Table 5–7 Participant Disposition Summaries

Parameter	Description	Timing	Methodology
Screening Period	Distribution in total for the Screened	Screening Period	Categorical
Disposition	Population		descriptives
Treatment Period	Distribution in total and by indication for	Treatment Period	Categorical
Disposition	the Safety Population		descriptives
	 Participants categorized based on 		
	latest available eCRF from the		
	Open-label, Double-blind, and		
	Dose-reduced Open-label		
	treatment periods		
Open-label Treatment	Distribution in total and by indication for	Open-label	Categorical
Period Disposition	the Safety Population	Treatment Period	descriptives
	Include distribution of participants who		
	discontinue who:		
	 do continue to Double-blind 		
	Treatment Period		
	 do not continue to Double-blind 		
	Treatment Period		
Double-blind Treatment	Distribution in total and by treatment	Double-blind	Categorical
Period Disposition	group within each indication for the	Treatment Period	descriptives
	Randomized Population		
	Include distribution of participants who		

Parameter	Description	Timing	Methodology
	discontinue who:		
	 do continue to Dose-Reduced 		
	Open-label Treatment Period		
	 do not continue to Dose-Reduced 		
	Open-label Treatment Period		
Dose-reduced Open-	Distribution in total and by treatment	Dose-reduced Open-	Categorical
label Treatment Period	group within each indication for the	label Treatment	descriptives
Disposition	Randomized Population	Period	

